#### **9.4.4 Nasopharyngeal Swab Results**

Nasopharyngeal swabs at Days 8, 15, 29, 43, and 57 are analyzed for SARS-CoV-2 by reverse transcriptase polymerase chain reaction (RT-PCR) and results are reported by time point and administration route for the Safety population.

### **9.5 Vital Signs, Physical Findings, and Other Variables Related to Safety**

#### **9.5.1 Vital Signs**

Vital signs parameters included blood pressure, heart rate, SpO2 (pulse oximetry), respiratory rate, and temperature. Vital signs were assessed at screening, on Day 1 (baseline) at pre-dose and 30 min and 1 hour after the end of dosing, and on Days 2, 3 (except IV arm), 4, 6 (except IV arm), 8, 15, 29, 43, and 57. Vital sign test results were assigned a toxicity grade by the investigator using the criteria in [11 Appendix I](#) as described in Section [5.8](#).

Vital sign data are summarized as follows for the Safety population:

- Shift from baseline in toxicity grade (Grade 0-4) are summarized (number and percentages) by study visit and treatment arm.

All vital sign records are provided in the subject data listings.

Anti-SARS-CoV-2 Immunoglobulin Intravenous (Human) (NP-028), abbreviated as COVID-HIG  
EBS-CVH-006 Statistical Analysis Plan

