6.6 Scheduled Study Visits

Day 2, 3, 4, 6, 8, 15, 29, 43

Visits are conducted as in-clinic or telemedicine/home healthcare follow-ups.

Visit windows are as follows (in relation to Day 1):

Day 2: (1 ± 0.5 days), Day 3: (2 ± 0.5 days), Day 4: (3 ± 0.5 days), Day 6: (5 ± 0.5 days), Day 8: (7 ± 1 day), Day 15: (14 ± 2 days), Day 29: (28 ± 2 days), Day 43: (42 ± 3 days).

*Visits are indicated as calendar days, while the time post-dosing and the visit windows are indicated in the brackets.

If randomized to IV group (Arm 3), omit visits on Day 3 and Day 6.

Perform the following in-clinic or via telemedicine follow-up:

- Assessment of AEs and concomitant medications (in-clinic or telemedicine).
- Targeted physical exam, if clinically indicated. Based on the investigator's assessment of AEs/concomitant medication during telemedicine follow-up, an unscheduled visit (in-clinic) can be arranged to conduct a targeted physical exam. The investigator can also refer the subject to their healthcare provider or urgent care if more immediate medical attention is required.
- If WOCBP, confirm use of contraceptives.
- Provide counseling to participants on precautions/measures to prevent contracting SARS-CoV-2 infection.
- Only if participant becomes positive for SARS-CoV-2 at any time post-dosing during the study period: assess clinical status based on an Ordinal Outcome scale ([Appendix II](#)). Perform assessments via telemedicine if possible.

Anti-SARS-CoV-2 Immunoglobulin Intravenous (Human) (NP-028), abbreviated as COVID-HIG
EBS-CVH-006, Version 3.0, 18 Feb 2022

In-clinic staff or home healthcare attendant to perform the following:

- Serum sample for SARS-CoV-2 antibody PK assessment.
- Blood sample for safety laboratory assessments (chem 7 panel, total and direct bilirubin, ALT, AST, LDH, CBC) at Day 2 and Day 4 only. At other follow-ups, collect sample only if clinically indicated (as per investigator's discretion).
- Sample for urinalysis at Day 2 and Day 4 only. At other follow-ups, collect sample only if clinically indicated (as per investigator's discretion).
- Vital signs (resting ≥ 10 minutes) [body temperature, blood pressure (seated), pulse, SpO₂ (pulse oximetry) and respiratory rate] at Day 2 and Day 4 only. At other follow-ups perform only if clinically indicated (as per investigator/sub-investigator's assessment).

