9.4.3.4 Vital Signs Test Results

Vital signs test results (including temperature, blood pressure, pulse, pulse oximetry, and respiratory rate) and change from baseline to Day 1 post-dose (from end of injection/infusion) time points, Day 2, and Day 4 will be summarized by time point and administration route for the safety population. The clinical significance of any abnormality will be assessed by the investigator, any abnormal vital signs results will be graded per [Appendix III](#). Vital signs can be repeated twice if grade 3 or higher to verify the severity. Values within the normal range as well as out of range vital signs values not meeting criteria for severity of at least grade 1 will be considered grade 0. Shift tables of vital signs severity grade (0, 1-2, ≥ 3) may be provided for selected parameters summarized by time point and administration route for the safety population.

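### SAP 9.5.1 plans only grade-shift tables for vital signs and omits the summary of values and change from baseline that Protocol 9.4.3.4 requires

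*SAP*

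**What the plan says.** **Protocol 9.4.3.4 (Vital Signs Test Results).** The required analysis covers vital-sign results and their change: "change from baseline to Day 1 post-dose (from end of injection/infusion) time points, Day 2, and Day 4 will be summarized by time point", by administration route, for the safety population. Shift tables in three bands (Grade 0, 1-2, 3 or higher) are optional; they "may be provided for selected parameters summarized by time point and administration route for the safety population".

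**SAP 9.5.1 (Vital Signs).** The section announces how vital signs are summarised for the Safety population and gives a single item: "Shift from baseline in toxicity grade (Grade 0-4) are summarized (number and percentages) by study visit and treatment arm". It then adds: "All vital sign records are provided in the subject data listings".

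**When vital signs were taken.** SAP 9.5.1 says they were assessed at screening, on Day 1 (pre-dose, 30 min and 1 h after dosing), "on Days 2, 3 (except IV arm), 4, 6 (except IV arm), 8, 15, 29, 43, and 57". Protocol 6.6 requires them at follow-up "at Day 2 and Day 4 only. At other follow-ups perform only if clinically indicated", and Protocol 6.8 makes the Day 57 reading conditional in the same way. The SAP's own schedule (Table 2, footnote 13) marks those later cells as conditional too.

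**The concern.** The table that the protocol makes mandatory is not in the SAP, and the one that it makes optional is the only one planned. The two are not interchangeable. A grade-shift table registers a change only when a reading crosses a grading limit, so a movement common to a whole arm can leave it blank. The readings at 30 min and 1 h exist to describe the acute response to dosing by each route. Protocol 5.1.4 counts small changes in pulse or blood pressure among the mild reactions that may occur during or just after injection. Safety of the IM and SC routes is a primary objective and every analysis is descriptive, so there is no other vital-sign analysis to fall back on.

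The second issue is one of wording. The text of SAP 9.5.1 lists all follow-up visits as if vital signs were routine at each, and then tabulates by visit. A programmer working from that section alone could produce percentages at visits where only a few selected participants were measured.

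**Working it through.** **1. Required against planned**

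| Analysis | Protocol 9.4.3.4 | SAP 9.5.1 |
|---|---|---|
| Observed values by time point and route | Required | Not listed |
| Change from baseline to Day 1 post-dose, Day 2, Day 4 | Required | Not listed |
| Grade-shift table | Optional, selected parameters | Only table planned |
| Subject listings | Not specified for vital signs | Planned |

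SAP 9.4.1 does commit to observed values and changes from baseline for haematology and chemistry, so the gap is specific to vital signs. SAP section 1 states that the SAP is based on Protocol Version 3.0, the version that contains 9.4.3.4.

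**2. What Grade 0 covers** (SAP Appendix I, same scale as Protocol Appendix III)

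- Systolic: hypotension Grade 1 is 85-89 and hypertension Grade 1 is 141-150, so Grade 0 is 90-140 mmHg; 140 − 90 = 50 mmHg wide.
- Pulse: bradycardia Grade 1 is 50-54 and tachycardia Grade 1 is 101-115, so Grade 0 is 55-100 beats/min; 100 − 55 = 45 wide.
- SpO2: Grade 1 starts below 95%, so 95% and above is Grade 0.
- Low diastolic pressure has no grade.

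Each of these hypothetical changes is therefore recorded as Grade 0 to Grade 0: systolic 130 to 92 mmHg (−38), pulse 60 to 100 beats/min (+40), SpO2 99% to 95% (−4 points).

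**3. How often would a shift table stay blank?** The documents give no expected vital-sign distribution, so this is an illustration. Assume baseline systolic is normal with mean μ = 115 to 125 and SD σ = 8 to 12 mmHg, and that every participant falls by d. Readings are whole numbers, so the Grade 0 limits are taken as 89.5 and 140.5. Given a Grade 0 baseline, the chance that one participant shows no shift is

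p = [Φ((140.5 − μ)/σ) − Φ((89.5 + d − μ)/σ)] / [Φ((140.5 − μ)/σ) − Φ((89.5 − μ)/σ)],

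and for an arm of n it is pⁿ. At μ = 120, σ = 10, d = 15: p = 0.939, and p⁷ = 0.645 before rounding p.

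| Uniform fall | n = 7: μ 120, σ 10 | n = 7: range | n = 8: μ 120, σ 10 | n = 8: range |
|---|---|---|---|---|
| 10 mmHg | 0.872 | 0.540 to 0.995 | 0.855 | 0.494 to 0.994 |
| 15 mmHg | 0.645 | 0.249 to 0.963 | 0.606 | 0.204 to 0.958 |
| 20 mmHg | 0.324 | 0.069 to 0.825 | 0.275 | 0.047 to 0.803 |

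A change-from-baseline table would show the fall directly.

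**4. Visits with conditional vital signs.** SAP 9.5.1 lists 9 follow-up visits. Days 2 and 4 are required, so 9 − 2 = 7 are conditional (Days 3, 6, 8, 15, 29, 43, 57). The IV arm has no Day 3 or Day 6 visit, so 7 are listed and 7 − 2 = 5 are conditional.

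**The case against.** **The data are still reported.** Every vital-sign record is listed by subject, and the study has 23 participants. A 38 mmHg fall can be found by reading the listing. This stands: a reader might infer that such changes disappear from the report, and the SAP does not support that. What is missing is the summary by time point and route.

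**The SAP leaves room for the table.** SAP 6.1 gives general descriptive statistics for continuous endpoints, 6.2 sets precision for vital signs and quantities derived from them, and 6.3 defines change from baseline. The table shells, which are not available here, may include it. None of these sections commits to a vital-sign table, and SAP section 1 describes the shells as a programming guide that can be updated. They do make a drafting omission as plausible as a decision, so the text does not show that the sponsor meant to reverse the protocol.

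**Vital-sign change is not an endpoint.** The listed safety endpoints are adverse events and serious adverse events. Investigators assess the clinical significance of abnormal vital signs, and events within 72 hours have their own table. This stands and limits the importance of the point. The imprecision of means with 7-8 per arm is also real, but the protocol asks for a description, not a test.

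**Conditional visits.** A reader might infer that the SAP claims routine measurement at every visit and will print misleading percentages based on symptomatic participants. The documents do not go that far. Footnote 13 of the SAP's schedule carries the restriction, SAP 9.5.2 uses the same shorthand for targeted examinations, the denominator is unstated, and the criterion is clinical indication at the investigator's discretion. What stands is that the text of 9.5.1 lacks a qualifier that SAP 9.4.1 gives for laboratory tests.

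**Conclusion.** The point holds as a departure of the SAP from the protocol. A required descriptive summary of vital signs is not planned, no reason is given, and the table planned in its place cannot summarise change within Grade 0. Those changes would be visible only in the individual listings.

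The size is modest: one missing table, with nothing lost from the data and no listed endpoint altered. The finding itself rests on a comparison of the two documents and on the printed grading limits. Only the blank-table probabilities depend on assumed systolic means and SDs and on a uniform fall, and their wide range shows that they illustrate the limitation without predicting anything for this study.

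The missing qualifier for conditional visits is a secondary matter of clarity. It does not follow that shift tables must be confined to the four post-dose time points through Day 4, because Protocol 9.4.3.4 sets no such limit on them.

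**What to change.** In SAP 9.5.1, add descriptive statistics of observed values and change from baseline at Day 1 30 min, Day 1 1 h, Day 2 and Day 4, by treatment arm, for the Safety population. Name the two Day 1 post-dose readings as separate time points, since tabulating by study visit leaves that open. The grade-shift table can stay as an addition. If the omission is intended, state the departure from Protocol 9.4.3.4 and the reason.

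In the same section, say that vital signs on Days 3, 6, 8, 15, 29, 43 and 57 were taken only if clinically indicated, following the model of SAP 9.4.1. For those visits, either show the number assessed as the denominator, or report the readings through worst post-baseline grade and the listings.

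The cost is one standard table from readings that the protocol already requires, plus a few sentences in the SAP. No new data are needed.

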Potential for injection-related local (e.g., pain, redness, tenderness or swelling) and systemic (back or abdominal pain, nausea and vomiting, fever, headache, myalgia, chills, rash, or fatigue) reactions.	These are common adverse reactions seen with other human hyperimmune products (VARIZIG, HepaGam B, ANTHRASIL, WinRho SDF, CNJ-016-VIGIV, BIVIGAM®, GAMMAPLEX®, Privigen®, GAMUNEX®-C, Hizentra®) (30, 31, 32, 33, 34, 35, 36, 37, 38, 39).	The IM dose will be administered to the thigh muscle and will be split between both thigh muscles to mitigate discomfort. All study participants will stay overnight in the inpatient unit for close observation for approximately 24 hours post injection. Injection stopping rules and study stopping rules are provided (Pharmacy Manual and Sections 3.4).
Potential for hypersensitivity reactions within six hours after the injection.	Hypersensitivity reactions are rare. Severe immediate hypersensitivity reactions to plasma-derived products occur in individuals with IgA deficiency or hypersensitivity to human globulin.	Participants will be monitored overnight after injection in a setting with appropriate equipment, medication and personnel trained in the management of hypersensitivity, anaphylaxis, and shock. Participants at risk of hypersensitivity reactions are excluded from the study.
Potential for renal dysfunction/acute renal failure.	Renal dysfunction has been associated with HIG products containing sucrose as a stabilizer.	COVID-HIG does not contain sucrose. Serum blood urea nitrogen and creatinine will be monitored at Screening and at Day 2 and Day 4 post-administration.
Potential for hematologic complications such as hemolytic anemia and thrombotic complications.	Rare thrombotic events have been associated with presence of activated factor XI resulting in elevated procoagulant activity in some immunoglobulin products. High doses (>1–2 g/kg) are associated with an increased risk of hemolysis.	COVID-HIG has been tested for procoagulant activity and has met the product release specification. The COVID-HIG doses being administered are well below 1 g/kg. Hemoglobin will be monitored at Screening and at Day 2 and Day 4 post-administration. Participants with pre-existing thrombotic or procoagulant disorders are excluded from the study.

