Potential for AMS or TRALI	AMS and TRALI rarely occurs in association with high doses (1–2 g/kg) of IGIV therapy. AMS begins within several hours to two days following	The COVID-HIG doses being administered are well below 1 g/day. Participants will be monitored overnight after injection, with safety tests at Days 2 and 4 post injection.

Anti-SARS-CoV-2 Immunoglobulin Intravenous (Human) (NP-028), abbreviated as COVID-HIG
EBS-CVH-006, Version 3.0, 18 Feb 2022

Potential Risk of Clinical Significance	Summary of Data/Rationale for Risk	Mitigation Strategy
	IGIV treatment, while TRALI occurs one to six hours post infusion.	
Potential for transmission of infectious diseases	Human plasma is used in the manufacture of COVID-HIG. Plasma is collected in accordance with regulatory requirements and donors are screened to assess the risk of exposure. Plasma donations are tested for HIV 1/2, HCV, and Hepatitis B.	Manufacturing processes include viral filtration and inactivation steps with quality control testing to eliminate risk of viral infection from COVID-HIG. Viral markers for Hepatitis B, Hepatitis C, and HIV 1/2 will be obtained from participants at Screening to document baseline status and at End of Study visit. Additional follow-up tests will be performed only if clinically indicated.
Potential for immunologic interference with live attenuated virus vaccine or the COVID-19 vaccine	Antibody therapies may impair the efficacy of live attenuated virus vaccines such as measles, mumps, rubella, and varicella. Concomitant administration of antibody therapies and the COVID-19 vaccine could theoretically result in immunologic interference.	The use of live virus vaccination before or after COVID-HIG should follow current recommendations. COVID-19 vaccination must occur at least 60 days prior to screening to be eligible. COVID-19 vaccination after the study should be deferred for 90 days post-administration as per current ACIP recommendations post-administration of passive antibody therapies (41)414141

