6.5.1 Acute Observation After Investigational Product Administration

The participant will be monitored by study staff for signs of an acute adverse reaction overnight in-clinic. Vital signs (resting ≥ 10 minutes) will be assessed at 30 minutes (± 5 mins) and 1 hour (± 10 mins) after administration.

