9.4.3.5 Nasopharyngeal Swab Results

Nasopharyngeal swabs at Days 8, 15, 29, 43, and 57 will be analyzed for SARS-CoV-2 by RT-PCR and results will be reported by time point and administration route for the safety population.

In addition, the frequency and percentage of participants testing positive for COVID-19 will be reported for the safety population. The maximum COVID-19 symptom severity per participant using an Ordinal Outcome grading scale ([Appendix II](#)) will be tabulated for the SARS-CoV-2 positive population.

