### **5.4 Analysis Time Points**

For PK analyses, SARS-CoV-2 antibody levels were assessed at screening, Day 1 (baseline) pre-dose and postdose (from end of infusion/injection) at 1 hr  $\pm$ 10 min, 2 hr  $\pm$ 15 min, 4 hr  $\pm$ 15 min, 8 hr  $\pm$ 30 min, and 12 hr  $\pm$ 30 min, Day 2  $\pm$ 0.5 day, Day 3  $\pm$ 0.5 day (excluding IV arm), Day 4  $\pm$ 0.5 day, Day 6  $\pm$ 0.5 day (excluding IV arm), Day 8  $\pm$ 1 day, Day 15  $\pm$ 2 day, Day 29  $\pm$ 2 day, Day 43  $\pm$ 3 day, and Day 57  $\pm$ 3 day. Since PK analyses use actual and not nominal day and time, out of window data entered as study visit data (i.e., not an unscheduled visit) are included in the analysis. In general, all available data are included in the summaries according to the analysis set defined for a subject's inclusion.

Data collected at unscheduled visits are not presented in the by-visit summary analyses but are included in the summary tables by maximum toxicity grade or abnormality when applicable, and in data listings.

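### Vital signs from unscheduled visits are listed but reach no vital-sign table, and the SAP does not say how extra inpatient readings on Day 1 are handled

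*SAP*

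**What the plan says.** SAP 5.4 sets the general rule: "Data collected at unscheduled visits are not presented in the by-visit summary analyses but are included in the summary tables by maximum toxicity grade". The sentence goes on to add abnormality tables, qualifies both by whether they apply, and adds data listings.

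SAP 9.4.1 gives laboratory values a destination under that rule: a table of each participant's highest grade at any time on study. SAP 9.5.1 gives vital signs one table, "Shift from baseline in toxicity grade (Grade 0-4) are summarized (number and percentages) by study visit and treatment arm", plus a listing of all records.

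SAP 5.6 covers vital signs too. Where a visit's analysis window holds several valid graded values, the by-visit summary takes the one with the highest grade.

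On timing, Protocol 6.5.1 says that Day 1 vital signs "will be assessed at 30 minutes" (±5 minutes) and again at 1 hour (±10 minutes). The next scheduled set is Day 2, at 1±0.5 days. Protocol Table 3 (Section 1.3.1) lists "Potential for hypersensitivity reactions within six hours after the injection". It also says, of aseptic meningitis syndrome and TRALI, that the former follows "IGIV treatment, while TRALI occurs one to six hours post infusion".

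For swabs, SAP 9.4.4 states that "results are reported by time point and administration route for the Safety population". Protocol 9.4.3.5 also promises that "the frequency and percentage of participants testing positive for COVID-19 will be reported for the safety population".

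**The concern.** Safety of IM and SC dosing is a primary objective, and the safety tables compare routes in arms of 7 or 8. SAP 5.4 assumes that a domain with unscheduled data may have a table to receive them. Laboratory values have one and vital signs do not, so for vital signs the rule ends in a listing.

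The adverse event tables only partly fill this gap. Under Protocol 8.2.2, a laboratory value that is Grade 3 or higher on retest or repeat is automatically an adverse event. No equivalent rule is stated for vital signs: Protocol 9.4.3.4 leaves clinical significance to the investigator, and there are no solicited events. A graded blood pressure, pulse, respiratory rate or SpO2 value that is not reported as an adverse event could therefore be missing from every summary by route.

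Day 1 adds an ambiguity. Much of the period in which the protocol places acute reactions falls between the last scheduled Day 1 reading and Day 2. Two programmers could treat an extra reading at, say, 3 hours differently, and both could claim to follow the SAP.

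**Working it through.** The SAP gives no figure to reproduce. The check sets its rules side by side and then does interval arithmetic on the schedule.

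**Where each kind of reading goes**

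| Reading | By-visit table | Maximum-grade table | Listing |
|---|---|---|---|
| Laboratory, unscheduled visit | No (SAP 5.4) | Yes (SAP 9.4.1) | Yes |
| Vital sign, scheduled visit | Yes (SAP 9.5.1) | None planned | Yes |
| Vital sign, unscheduled visit | No (SAP 5.4) | None planned | Yes |
| Extra inpatient vital sign, Day 1 | Undefined (SAP 5.4, 5.6) | None planned | Yes |

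The fourth row is undefined for two reasons. SAP 5.4 is worded for unscheduled visits, and the participant is still an inpatient, so the exclusion does not clearly apply. SAP 5.6 would pick the worst value within an analysis window, but neither SAP 5.4 nor 9.5.1 gives a Day 1 window for vital signs that extends beyond the 1-hour reading.

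**Coverage of the acute-reaction periods**

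Inputs, in minutes after the end of dosing:
- Scheduled windows: 30±5 gives 25 to 35; 60±10 gives 50 to 70; Day 2 at 1±0.5 days gives 720 to 2,160.
- TRALI period 60 to 360, length 300. Hypersensitivity period 0 to 360, length 360.

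The formula is uncovered time = period length − overlap with the scheduled windows.
- TRALI: the overlap is 70 − 60 = 10. Uncovered = 300 − 10 = 290 minutes, and 290/300 = 96.7%.
- Hypersensitivity: the overlap is (35 − 25) + (70 − 50) = 30. Uncovered = 360 − 30 = 330 minutes, and 330/360 = 91.7%.
- Gap from the end of the 1-hour window to the opening of the Day 2 window: (720 − 70)/60 = 10.8 hours. Nominally it is 24 − 1 = 23 hours.

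These are shares of clock time without a scheduled reading. They are not shares of readings taken or lost, which the documents do not allow one to estimate.

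**Weight of one participant**

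One participant with an untabulated graded value is 1/8 = 12.5 or 1/7 = 14.3 percentage points of an arm.

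**Swabs**

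Protocol 9.4.3.5 plans two summaries in the Safety population: results by time point, and participants testing positive. SAP 9.4.4 carries over only the first, for Days 8, 15, 29, 43 and 57. Protocol 6.7 allows swabs at unscheduled visits, and SAP 5.4 would keep those out of a by-visit table. After a positive test, visits move to telemedicine except Day 57 or withdrawal, so later scheduled swabs may not show the case.

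**The case against.** A reader might infer that readings taken 1 to 6 hours after dosing appear in no safety table. The documents do not support that, for four reasons:
- The scheduled 1-hour reading is in the shift table.
- Participants stay on the ward until the 24-hour assessments are done, and unscheduled visits are a separate encounter with their own case report form. An extra Day 1 reading is therefore not plainly excluded, and SAP 5.6 could make it the value tabulated.
- A reaction recorded as an adverse event enters the adverse event tables, including those for events within 72 hours (SAP 9.2.1).
- Every vital-sign record is listed.

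The qualifier in SAP 5.4 also means that it does not promise a maximum-grade table for every domain, and Protocol 9.4.3.4 does not promise one for vital signs. Table 3 describes potential risks, calls hypersensitivity rare, and ties rare TRALI to 1–2 g/kg, against the roughly 8–16 mg/kg given in Protocol 2.1.1. The table shells that accompany the SAP were not available and might include such a table, although SAP Section 1 describes them as a guide only.

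All of this stands, and it narrows the point. It does not supply a table for unscheduled-visit vital signs or a rule for extra Day 1 readings. Nor does it ensure that every graded value becomes an adverse event.

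On swabs, a positive can be recovered indirectly. SAP 5.1.1 treats COVID-19 as an adverse event, SAP 9.2.4 tabulates it, and SAP 8.1 counts the SARS-CoV-2 Positive population. That population is analysed by randomized arm and may include undosed participants, so it is not the same count as the protocol's. The 1-to-6-hour period has no bearing on swabs.

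**Conclusion.** The concern holds in a limited form. Followed as written, the SAP lists vital signs from unscheduled visits but does not tabulate them. It leaves undefined whether an extra Day 1 reading taken after the 1-hour set can enter the by-visit table. The undefined stretch includes 290 of the 300 minutes between 1 and 6 hours.

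The gap affects graded values that are not reported as adverse events. How many there are cannot be known from the documents. If there were one in an arm, it would be 12.5 to 14.3 percentage points of that arm. The conclusion assumes that the shells add no worst-grade table and that the risk periods in Table 3 run from about the same time zero as the scheduled readings.

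In a descriptive study of 23 participants with full listings and adverse event tables, this is a reporting gap that is cheap to close. It does not invalidate the safety analysis. The missing ever-positive swab count is a lesser matter, because it only leaves out a summary that the protocol promised.

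**What to change.** In SAP 9.5.1, add a participant-level table of the worst post-dose toxicity grade for each vital sign, mirroring the laboratory table in 9.4.1:
- Present it by actual route for the Safety population, with high and low directions separate where the grading scale has both (pulse, systolic pressure).
- Include all scheduled and unscheduled post-dose readings, and say in the title or footnote that symptom-driven readings are included.
- State how repeats taken to verify a Grade 3 or higher value are counted.

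Add one sentence to SAP 5.6 saying whether extra Day 1 readings can be selected for the by-visit shift table. Either answer is workable once the worst-grade table exists.

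In SAP 9.4.4, restore the Protocol 9.4.3.5 summary: number and percentage of Safety-population participants ever RT-PCR positive after dosing, on a scheduled or unscheduled swab, by route.

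The cost is one new table, one added row and short SAP wording, all from data already collected, with no change to visits or clinical procedures. The drawback is that readings prompted by symptoms are not comparable with scheduled ones, which is why the label is needed. If the tables have already been produced, report these as additions to the approved SAP.
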